The principal investigator, investigator 1 and 2, and technician 1, as well as the participants who will form the different groups consuming the chewing gums, will be unaware of the type of gum (double-blind). Both the chewing gums and the paraffin will have the same weight (1.3 g), and the blinding method will involve the presence of identical, pre-numbered containers containing the different chewing gums. This information will only be accessible to technician 2. Saliva samples will be collected by the principal investigator, and the data will be recorded on a form specifically designed for this purpose by technician 1, which will be executed in the Molecular Biology laboratory (**Appendix E - Data Collection Form**).

7.3 Saliva Sample Collection: Saliva samples will be taken between 8 to 10 am, ensuring that subjects have not ingested food, smoked, or brushed their teeth at least 1 hour prior to sample collection. Participants will be asked to rinse their mouths with pure water to remove any food residue. Subsequently, they will be seated in a chair in an upright position with their head slightly tilted forward and eyes open, and the basal saliva sample will be taken as indicated by the established protocol for collecting unstimulated saliva by Tomas Seif. Before starting the test, participants will be asked to swallow saliva. They should keep their mouth slightly open and allow saliva to drain into the tube. The test will last five minutes, during which salivary pH will be evaluated and weighed, denoted as T1. For stimulated saliva, the protocol dictated by the Faculty of Dentistry at the University of Southern California will be used, utilizing the drainage method. Stimulated saliva will be collected in another pre-weighed test tube at three additional time intervals: T2 from 5 to 10 minutes, T3 from 15 to 20 minutes, and T4 from 25 to 30 minutes after the start of chewing gum consumption. Salivary flow and pH level measurements will be evaluated immediately using a pH meter (BT-675 meter, Boeco-Germany), performed by the principal investigator. Sample collection will be conducted over a period of two weeks.

Figure 2. Random allocation of participants for the determination of salivary flow and pH level. 7.4 Operation mechanism of the desktop pH meter BT-675 BOECO-Germany

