7.7 Information Management: Technician 1 will handle the physical documents until the laboratory process is completed. Subsequently, Technician 1 will provide the data matrix in Excel for further analysis by Investigator 1. Participants will not receive individual research results; instead, the final research results will be disseminated.

8. Human biological samples do not require exportation as they will be disposed of immediately after the determination of salivary flow and pH level.

9. Data Analysis Plan

The data analysis will be conducted using SPSS v.25. Descriptive analysis of the data will be performed. Chi-square test will be used for demographic data, Levene's test will determine the homogeneity of the data, and ANOVA test will be used to determine differences in means. Post-hoc Tukey's test will be employed to find significant differences between the means of the groups, with a significance level set at p<0.05. All analyses will be conducted by Investigator 1.

HUMAN AND MATERIAL RESOURCES

1. Enumerate the human resources that will participate in the research, detailing the functions each one will fulfill; it should coincide with the section.

1. Principal Investigator		Collecting the sample and measuring salivary flow and pH		
2. Investigator 1	Inviting participation via email and conducting statistical analysis			
3. Investigator 2	Sending study participation information via email.			
4. Technician 1		Collecting quantitative data on the data sheets.		
5. Technician 2		Collecting the sample.		

2. Provide a detailed description of all the material resources used for the execution of the project, including necessary information

Among the materials are nitrile gloves, masks, Falcon tubes, funnel, hand towels, xylitol chewing gums, Trident, Agogo, and paraffin. As for the equipment, a pH meter and a precision scale (Boeco) are needed.

ETHICAL AND GENDER CONSIDERATIONS

1. Provide a detailed description of the measures to be taken to ensure the rights of individuals to minimal risk, autonomy, and confidentiality

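### The only holder of the gum code is also listed as a sample collector, and the double-blind label is wider than the stated masking supports

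*Protocol*

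**What the plan says.** Section 7.2 lists those kept blind: "The principal investigator, investigator 1 and 2, and technician 1, as well as the participants", limited to participants in the groups that chew gum, who "will be unaware of the type of gum (double-blind"). Technician 2 is not in that list. On access to the container code and on collection, the section continues: "This information will only be accessible to technician 2. Saliva samples will be collected by the principal investigator".

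The masking consists of two measures. One is matched weight: "Both the chewing gums and the paraffin will have the same weight (1.3 g"). The other is packaging: "the blinding method will involve the presence of identical, pre-numbered containers containing the different chewing gums".

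The staff table under Human and Material Resources gives the principal investigator "Collecting the sample and measuring salivary flow and pH" and gives technician 2 only "Collecting the sample". The form's instruction above the table asks that the listed functions agree with another section of the form. Keeping the code does not appear in the table for anyone.

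The summary and the Research Design entry both call the trial double-blind without qualification. The fourth group chews paraffin.

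**The concern.** Two places in one protocol assign the same task differently, and the difference falls on the one person who knows the allocation. Under section 7.2 the blinded principal investigator collects. Under the staff table the code holder collects too. A team that follows the table would bring the unblinded person to the chairside while saliva drains into the tube.

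What is at stake is the flow result. Flow comes from the weight of saliva collected in a fixed window. Blinded weighing afterwards does not undo an influence on what entered the tube. Staff roles and blinding are fixed in a protocol, so a statistical analysis plan would not be expected to resolve this.

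The second, smaller issue is the label. If readers take double-blind to mean that every participant is blind, they will credit the gum-versus-paraffin flow comparisons with more protection than the text provides.

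**Working it through.** The protocol gives no figure for this point, so the check is mainly a comparison of passages.

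**Roles, side by side**

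| Item | Section 7.2 / 7.3 | Staff table |
|---|---|---|
| Holds the code | Technician 2 only | Not mentioned |
| Declared blind | Principal investigator, investigators 1 and 2, technician 1, gum-chewing participants | Not mentioned |
| Collects saliva | Principal investigator | Principal investigator and technician 2 |
| Measures flow and pH | Principal investigator | Principal investigator |

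The two sources agree on measurement and disagree on collection. The table does not say which part of collection technician 2 performs. Nothing elsewhere in the protocol keeps technician 2 away from the drainage.

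**Which outcome is exposed**

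- pH: section 7.4, step 5, describes a reading that locks once stable, and the principal investigator takes it. There is little room for influence.
- Flow: section 7.3 collects stimulated saliva by drainage into pre-weighed tubes at T2, T3 and T4 (5 to 10, 15 to 20 and 25 to 30 minutes after chewing starts). The collection step itself determines the result.
- Arms: a code holder knows the product in every arm, so the role conflict does not single out paraffin. At the planned size it covers 25 × 4 = 100 participants and 100 × 3 = 300 post-chewing tubes.

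**What the masking can conceal**

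Equal weight and identical containers work until the product is in the mouth. The summary lists sweeteners in all three gum arms. The background section counts sweet taste among the ways gum raises salivary flow. The protocol thus treats taste as perceptible and as relevant to flow, but states no measure that matches taste or texture between paraffin and gum.

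**Comparisons that involve paraffin**

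This takes Tukey comparisons of flow among the four groups at each of T2, T3 and T4, which is an assumption because the analysis section does not specify the time points.

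- Pairs among four groups: 4 × 3 / 2 = 6.
- Pairs that include paraffin: 3.
- Over three post-chewing times: 3 × 3 = 9 of 6 × 3 = 18.
- Paraffin tubes: 25 × 3 = 75 of 300.

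This count belongs to the labelling point only.

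**The case against.** The strongest reply is that the table entry may be innocent. Technician 2 might only hand over or label tubes. Measurement is blinded in both places, the tubes are pre-weighed and the windows are fixed. All of that stands, and it limits the consequence. It does not remove the contradiction, because the table is unspecific and no sentence keeps the code holder out of collection.

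On participants, section 7.2 speaks of those in the gum-chewing groups and of the type of gum. Read literally, it does not clearly claim that the paraffin arm is blind. That is fair. What remains is the unqualified label in the summary and under Research Design. That paraffin users can tell the difference is an inference: the text does not describe how the paraffin tastes. The appendix on the products is not at hand and might describe further masking, but that would not settle the role conflict.

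Three stronger readings are tempting and are not supported:

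- A reader might infer that the collector can easily coach the post-chewing samples because of the instruction "They should keep their mouth slightly open and allow saliva to drain into the tube". That instruction belongs to the unstimulated T1 sample. Stimulated saliva follows a separate external protocol that is not reproduced, so the scope for influence there cannot be judged.
- A reader might want an inflated false-positive rate. The document offers no bias to put into such a calculation. Any answer would rest on an invented shift and on the choice between the flow standard deviations cited in the Research Problem section (0.31 to 0.45) and the planning variance of 1.
- A reader might conclude that blinding fails between the gums as well. Tasting a gum is not the same as knowing which product it is, and the text does not show that participants could identify it.

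**Conclusion.** The contradiction holds on the face of the text. Section 7.2 makes technician 2 the sole code holder and gives collection to a blinded person, while the staff table makes technician 2 a collector. The exposure is mainly to salivary flow and applies in all four arms. Its size cannot be derived from the document and may be zero. pH is largely protected by the locked reading and blinded measurement.

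The labelling point is secondary. It qualifies the double-blind claim for the paraffin arm, which enters 9 of the 18 post-chewing pairwise flow comparisons. It rests on the inference that paraffin and sweetened gum feel or taste different when chewed. Neither point shows that bias will occur or that the trial is invalid.

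**What to change.** 1. Reconcile section 7.2 with the staff table so that whoever holds the code takes no part in saliva collection or measurement. There are two workable ways. One is to remove technician 2 from collection and list code-keeping as that person's function. The other is to move the code to an existing staff member with no collection, measurement or analysis role, for example investigator 2, whose only listed task is sending study information by email.
2. Correct the blinded list in section 7.2 to match. Under the second option technician 2 joins the list and investigator 2 leaves it.
3. In the summary and under Research Design, qualify the double-blind label: state which roles are blind and that participants in the paraffin arm are not assumed to be. Interpret gum-versus-paraffin flow comparisons accordingly.

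Cost: wording changes and a small reallocation of work, but not necessarily zero time. Collection runs from 8 to 10 am for two weeks. Assuming 10 weekdays, 100 / 10 = 10 participants a day. Each needs at least 5 + 30 = 35 minutes, so at most three consecutive slots fit into 120 minutes (3 × 35 = 105). Since 10 / 3 = 3.3, up to four participants must be seen at once. The principal investigator may therefore need a second collector. Moving the code keeps technician 2 available for that, while removing technician 2 means that other blinded staff must help. The remaining downside is a more modest blinding claim.

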Chewing gum stimulates salivation, neutralizes, and raises pH levels, serving as a medium for administering therapeutic agents. However, global increases in sugar consumption have led to the development of chewing gums containing sugar substitutes such as polyols or non-fermentable sugars, with the most common being nutritive sweeteners like sorbitol and xylitol. The use of polyolcontaining chewing gum could play a role in preventing dental caries compared to not using gum or using sugared gum, most likely due to increased salivary flow and pH, thereby improving enamel lesion remineralization. However, xylitol has anticariogenic properties influencing the reduction of dental plaque. Objective: To evaluate the effects of xylitol-based chewing gum, both sugar-free and sugared, on salivary flow and pH in young adults. Methodology: This is a quantitative, analytical, experimental study through a double-blind parallel randomized controlled trial. The population will consist of all students enrolled (1275 students in the period October 2022-February 2023) in the Dentistry program at the Catholic University, aged 18 to 25, who voluntarily meet the inclusion criteria. The sample size will be 21 participants in each group, adjusted for a 15% loss of information or study dropout, thus requiring 25 participants in each group. Participants meeting the selection criteria will be assigned probabilistically using simple random sampling through a lottery system to four groups: the first group (G1) will consume gum with 100% xylitol, the second group (G2) will consume sugar-free gum with sorbitol, maltitol, mannitol, and xylitol, the third group (G3) will consume sugared gum containing sugar, dextrose, glucose, sweeteners such as aspartame and acesulfame-K, and the fourth group (G4, control) will chew paraffin. Data will be entered into an Excel matrix and analyzed using SPSS v.25. Descriptive analysis of the data will be conducted. Chi-square will be used for demographic data, Levene's test will determine data homogeneity, and ANOVA will determine mean differences, followed by Tukey's post-hoc comparison to find significant differences between group means, with a significance level of p <0.05. Expected Results: It is expected that salivary pH and flow means will differ among the different chewing gums.

RESEARCH PROBLEM

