Global increases in sugar consumption have prompted the development of sugar substitutes, including polyols or non-fermentable sugars, of which the most commonly used are nutritive sweeteners like sorbitol and xylitol. Chewing gum is a means to administer therapeutic agents and contribute to improving oral conditions. In the national market, there are sugared chewing gums (sucrose) and sugar-free gums that include xylitol plus sorbitol. These gums are consumed in high quantities, especially by teenagers and young adults, and the few studies conducted in Ecuador indicate a significant elevation in salivary pH from 6.4 to 7.14^{7,8} after consuming sugar-free chewing gums, compared to sugared gums. However, these investigations evaluate salivary pH levels using reactive strips. Additionally, there are no locally available chewing gums solely based on xylitol, and there are also sugar-free chewing gums that use a blend of compounds as sweeteners without indicating the percentages. Therefore, high-quality randomized controlled trials are needed to determine the effectiveness on salivary pH.

A study conducted in India⁵ compared the efficacy of two sugar-free chewing gums. The first group showed a significant increase in salivary pH levels up to 2 minutes after consuming sugar-free chewing gums (pH 7.98 \pm 0.19), which gradually decreased to 7.60 \pm 0.12 at 30 minutes, compared to another group of sugar-free chewing gums where salivary pH levels at two minutes were higher (pH 7.49 \pm 0.16) than at 30 minutes (pH 6.82 \pm 0.28), showing statistically significant differences within each group. Regarding salivary flow, there was a higher average at two minutes (1.89 \pm 0.42), which gradually decreased to 1.09 \pm 0.31 at 30 minutes (1.89 \pm 0.45), which decreased to 1.04 \pm 0.31 at 30 minutes, showing statistically significant differences.

Therefore, chewing gums stimulate an increase in salivary flow, which contributes to diluting and cleaning the oral cavity, as well as buffering and allowing ionic exchange. Additionally, they promote a neutral or alkaline salivary pH level, which may contribute to enamel remineralization and, therefore, prevent dental caries.² Furthermore, they could serve as a complement to oral hygiene in situations where tooth brushing is not possible.

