Based on the above, the following question is raised: Does the consumption of xylitol-based chewing gums positively influence salivary flow and pH compared to sugared or sugar-free gums?

JUSTIFICATION

This research is focused on determining the effects of xylitol-based chewing gums (100% xylitol, Xylichew brand), sugarfree gums (sorbitol, maltitol, mannitol, and xylitol, Trident brand), and sugared gums (sugar, dextrose, glucose, sweeteners such as aspartame and acesulfame-K, Agogó brand) on salivary flow and pH in young adults: a randomized controlled trial in students of the Dentistry Career at the Catholic University of Cuenca, 2023. In our context, the distribution of sugar-free gums includes xylitol and sorbitol among its ingredients, without indicating the exact proportions of each. Additionally, there are no chewing gums in the Ecuadorian market that contain xylitol as the sole ingredient, hence the need to compare with a foreign chewing gum, which indicates the presence of only xylitol.

Vantipalli et al.⁵ showed statistically significant differences between two sugar-free chewing gums in terms of unstimulated salivary pH and salivary pH stimulated at 2 minutes, showing an increase at this time compared to 30 minutes after gum consumption. Similar results were reported for salivary flow, showing a higher flow at two minutes compared to 30 minutes after gum consumption. This study demonstrates significant changes within each group and between subgroups for salivary pH levels, while salivary flow showed significant changes only within each gum group evaluated.

This study has a degree of originality, as there are studies conducted in Ecuador that found significant changes with an increase in salivary pH levels in chewing gums containing sorbitol and maltitol. However, they did not evaluate chewing gum containing xylitol as the sole ingredient, and they used reactive strips as equipment to evaluate salivary pH. Therefore, high-quality and appropriate equipment is needed to determine salivary pH, and the Molecular Biology Laboratory has a pH meter, providing a precise tool for assessment.

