Xylitol is considered cariostatic due to its ability to decrease counts of Streptococcus mutans (SM)^{12,14} and Lactobacillus (LB)⁴, as well as its role in controlling dental plaque formation and, consequently, the incidence of dental caries. Therefore, it is particularly effective in conditions where proper oral hygiene is not possible¹², or as a complement to toothbrushing for oral hygiene.^{14,15} Additionally, it stimulates salivary secretion, an important factor in maintaining alkaline pH, and promotes mechanical cleansing of tooth surfaces.¹³

Its mechanism of action is to create an unfavorable environment for bacterial growth, especially for Streptococcus mutans (SM), as it reduces its ability to adhere to oral tissues by affecting the insoluble glucans involved in this process. This property reduces the possibility of dental plaque formation and, therefore, the local effect of lactic acid. Additionally, xylitol penetrates the bacterial

cytoplasm, interfering with glycolysis and inhibiting the growth of microorganisms.¹²

Furthermore, its action affects other species such as Streptococcus sobrinus (SS) and Actinomyces viscosus (AV). As a result, a less cariogenic environment is created. ¹² Tapiainen et al. ¹⁶ stated that the effect of xylitol disappears from saliva within 15 minutes.

Sorbitol is a hexitol derived from glucose with low cariogenic potential. Like xylitol, it causes a decrease in SM, SS, AV, LB, and insoluble glucans, along with an increase in salivary pH, giving it anticariogenic potential. Current evidence establishes that pentitols like xylitol, as well as hexitols like sorbitol, have good results in reducing dental caries. However, pentitols are more effective and therefore more commonly used. ^{4,12}

RESEARCH OBJECTIVES

General Objective

Compare the effects of xylitol-based chewing gum (Xylichew), sugar-free (Trident), and sugared (Agogó) on salivary flow rate and pH in young adults

Specific Objectives

Determine the initial salivary flow, at 10, 20, and 30 minutes after the consumption of xylitol-based, sugar-free, and sugared chewing gums in young adults.

Determine the initial salivary pH, at 10, 20, and 30 minutes after the consumption of xylitol-based, sugar-free, and sugared chewing gums in young adults.

RESEARCH QUESTION OR STUDY HYPOTHESIS

H0: The consumption of different chewing gums does not produce changes in the level and flow of initial salivary pH at 10, 20, and 30 minutes.

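### Section 9 compares group means by ANOVA without using T1 and names no lead outcome or time, while H0/H1 are worded as change from the initial value

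*Protocol*

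**What the plan says.** - **Planned test.** Section 9 (Data Analysis Plan) states that "ANOVA test will be used to determine differences in means" and that Tukey's test "will be employed to find significant differences between the means of the groups", at p<0.05. The Methodology part of the summary repeats this: Tukey's "post-hoc comparison to find significant differences between group means". Neither place mentions time or T1, or says which kind of ANOVA is meant.
- **Data.** The Methodology section lists salivary flow and salivary pH at four periods. Section 7.3 takes T1 unstimulated before chewing, then T2 (5–10 minutes), T3 (15–20) and T4 (25–30) from the same person during stimulation.
- **Hypotheses.** H0 is that consuming the different gums "does not produce changes in the level and flow of initial salivary pH at 10, 20, and 30 minutes". H1 is the same statement in the affirmative.
- **Question and aims.** The research question is comparative: "Does the consumption of xylitol-based chewing gums positively influence salivary flow and pH compared to sugared or sugar-free gums". The general objective is to compare the three gums, and the expected results in the summary are that pH and flow means differ among gums.
- **Sample size.** 21 per group (25 after 15% loss) for a difference of 1 with variance 1. The outcome and time to which that unit belongs are not given.

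**The concern.** Two things do not fit together.

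First, H0/H1 read literally concern movement away from the initial value, but the planned test compares groups with each other. These are different hypotheses, and one can be true while the other is false. Because T1 is unstimulated and T2–T4 are stimulated, a rise shared by all groups is quite possible, so the difference is not academic.

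Second, two outcomes at three post-chewing times can be tested, and nothing marks one of them as the test on which the trial's conclusion rests. The sample size does not settle it either. An isolated positive result would be hard to interpret, and the choice of what to emphasise could be made after the data are seen.

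A lesser matter is that a baseline is collected from everyone and then given no role in the analysis.

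**Working it through.** **1. The plan's own sample size.** Inputs from the Methodology section: Zα = 1.96, Zβ = 1.282, S² = 1, d = 1.
n = 2(1.96 + 1.282)² × 1 / 1² = 21.02. The printed 20.99 corresponds to Zβ = 1.28, so the difference is rounding. Allowing for 15% loss, 21/0.85 = 24.7, i.e. 25. The stated figures reproduce. The implied effect is d/S = 1 SD.

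**2. Is the simple reading valid?** A separate one-way ANOVA at each time uses one value per person in independent randomised groups. Each F test keeps its 5% error, and Tukey covers the six pairs within it. Pooling the three post-chewing times as if they were independent rows would not be valid: in simulation the type I error was about 18%, 28% and 36% at within-person correlation 0.3, 0.5 and 0.7. The per-time reading is therefore used below.

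**3. Number of tests and overall error.** 2 outcomes × 3 times = 6 F tests (8 if T1 is tested as well). If all six were independent: 1 − 0.95⁶ = 26.5%.

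The tests are correlated, and the protocol gives no correlations, so a range is assumed. Simulated chance of at least one p<0.05 under the global null (4 × 21, equal correlation between times, 40,000 runs):

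| Within-person correlation | One outcome, 3 times | Both outcomes, between-outcome correlation 0 | Both outcomes, between-outcome correlation 0.7 |
|---|---|---|---|
| 0.3 | 14% | 25–26% | 22–23% |
| 0.5 | 13% | 24% | 21% |
| 0.7 | 11–12% | 22% | 19% |
| 0.9 | 9% | 17% | 14% |

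Across the table, both outcomes together give about 14–26%. One named outcome at one named time gives 5%.

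**4. Hypothesis against test.** Suppose all four groups rise by the same amount c from T1. The literal H0 is then false. Adding c to every group mean leaves the between-group mean square unchanged, so F keeps its null distribution and rejects about 5% of the time. The planned test cannot answer H0 as worded.

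**5. What T1 could add.** Inputs: four groups, 21 per group, 1 SD gap between two groups. The Tukey critical value on the t scale is q/√2 = 2.62.
- Without T1: noncentrality √(21/2) = 3.24, df 80, power 73%.
- With T1 as covariate at T1–outcome correlation ρ: noncentrality 3.24/√(1 − ρ²), df 79. At ρ = 0.1 / 0.3 / 0.5 this is 3.26 / 3.40 / 3.74, giving power 73% / 78% / 86%.
- A simulated ANCOVA with Tukey that includes chance imbalance in T1 gives 72.8% / 76.7% / 85.9%, with familywise error 5.1–5.2%.
- Sidak for the six pairs (critical value 2.70): 71% / 76% / 85%.

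**The case against.** **Much of this could sit in a statistical analysis plan.** The form of the ANOVA, a covariate and the multiplicity method are often left there, and such a plan may exist. That stands for T1, which alone would be a minor point. It does not cover a stated hypothesis that differs from the stated test, nor the absence of a lead outcome and time from the hypotheses, objectives and sample size.

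**Six tests is one reading.** A group-by-time repeated-measures ANOVA is also an ANOVA. It would give T1 a role, and its interaction would compare change between gums. That stands: six is a derived count. But Section 9 names no time factor, and under either reading neither pH nor flow leads.

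**The intended question is clear and H0/H1 are only badly worded.** Largely true, so the remedy is an edit.

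**The power case for T1 assumes a 1 SD gap.** The Research Problem section reports pH 7.98 ± 0.19 and 7.49 ± 0.16 at 2 minutes for two sugar-free gums. The gap is 0.49 over a pooled SD of √((0.19² + 0.16²)/2) = 0.18, or about 2.8 SD. If such gaps recurred, T1 would not be needed for power. The 1 SD figure is the protocol's own design value, but the gain from T1 should not be oversold.

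**Stronger readings a reader might infer.**
- That the planned ANOVA is invalid or biased. Run at each time in randomised groups, it is neither.
- That T2 must lead because "the effect of xylitol disappears from saliva within 15 minutes". That remark closes an account of antibacterial action, is not tied to pH or flow, and does not say when the 15 minutes begin.
- That a joint mixed model over T2–T4 is required. At one time with complete data, the precision comes from T1 and not from joining the times.

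**Conclusion.** The point holds in this form. Section 9 leaves T1 unused and fixes no lead outcome or time, and H0/H1 do not state the question that the test answers. The gum comparisons at any one time remain unbiased, and the sample size reproduces.

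The overall chance of at least one false positive is about 14–26%. This rests on the per-time reading of an unspecified ANOVA, on assumed within-person correlation of 0.3–0.9 and on assumed between-outcome correlation of 0–0.7. The mismatch between hypothesis and test follows from the wording and needs no numerical assumption.

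The gain from T1 ranges from none (73% power at correlation 0.1) to 13 points (86% at 0.5) for a 1 SD gap at 21 per group. Because T1 is unstimulated, low correlation is plausible and the gain may be nil to small. The unnamed lead test and the hypothesis wording carry the finding. The unused T1 is secondary.

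**What to change.** Before data are seen:
1. Name one primary outcome (pH or flow) and one primary time (T2, T3 or T4), and say why.
2. Analyse it by ANCOVA with group and the T1 value of the same outcome, with the six group comparisons Tukey- or Sidak-adjusted.
3. Label the other outcome and the other times secondary.
4. Reword H0/H1 as no difference / a difference between the four groups in post-chewing pH (or flow), adjusted for T1. Report change from T1 within groups descriptively.
5. State in the sample-size paragraph the outcome and time to which the 1-unit difference refers.

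This changes wording only: no new samples or visits, and 21 per group (25 with loss) stands on the protocol's own formula. The price is commitment: an effect found only at another time or on the other outcome counts as secondary. If Tukey with a covariate is awkward in the software, Sidak costs about 2 points of power.
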